### PROTOCOL

---

Proprietary and confidential property of UnitedHealth Group. Do not distribute. OHRA Template V.04/2021

Version	Date	Notes	Initials
1.0	8/6/21	Version 1 draft	kc
1.1	9/24/21	Response to IRB feedback	kc
1.2	9/29/21	Update study name to Breath Monitor	HB
1.3	04/19/22	Update recruitment to up to 350 from 300	CC

SYNOPSIS	
Tracking IDs	OHRA protocol number, 2021-0056
Full Title (Scientific)	Breath Monitor Carbon Monoxide Monitoring Study
Short Title (Public Facing)	Breath Monitor Study
Type of Project Description	Interventional Research
Focus Area/Category	Product Development
Primary Objective	Conduct a 3-arm randomized pilot study to determine the value of adding CO Monitoring (with and without financial incentives) to standard Quit For Life tobacco cessation service offerings.
Anticipated Duration	Launch: 10/2021 -- Publication: 06/2023
Primary Target Population	Quitline callers who 18+ years old from participating states who are current smokers

PERSONNEL – FULL NAME, CREDENTIALS, AFFILIATION, EMAIL ADDRESS	
Principal Investigator	[name]., Optum Health, [contact]
Owner/Primary Contact	[name], Optum Health, [contact]
Clinical Lead	[name], MS, Optum Health/Rally, [contact] (She will be moving to Optum proper 9/26/21)
Data Scientist	TBD
Operations Architect	NA
Internal Sub-Investigators	[name], MS
External Sub-Investigators	None

## 1. SPECIFIC AIMS

### Aim 1 + Hypothesis 1:

Conduct a 3-arm randomized pilot study to determine the value of adding carbon monoxide (CO) monitoring (with and without financial incentives) to standard Quit For Life tobacco cessation service offerings. We hypothesize that the CO monitoring will be feasible and acceptable to deliver (measured by app download rates and CO compliance rates).

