## PROTOCOL

CO testing has also been identified as a valuable monitoring and feedback component of effective stop smoking programs and benefits cessation through making the health impact of smoking more salient. Smaller and more affordable CO monitors have made CO monitoring feasible for home use. The iCOTM Smokerlyzer® manufactured by Bedfont® Scientific Ltd. (Harrietsham, UK) is currently the only such device available for purchase. It connects to smartphones via bluetooth and requires a dedicated app to compute and display CO levels. This provides momentary feedback on behavioral outcomes, which are important self-regulatory and behavior change techniques in smoking cessation. Preliminary research suggests that personal use of CO monitors is acceptable, valued and potentially highly motivating for smokers. No large scale studies of CO monitoring as a component of a comprehensive tobacco cessation program have been published.

**Vincere Health (VH; [www.vincere.health](http://www.vincere.health))** is a small business who joined United Healthcare's (UHC) Accelerator program in 2020. VH has developed a proprietary smartphone app that transforms data from the Bedfont CO monitor (cited above) into user-friendly pictorial displays and graphs. The app also connects to coaches, offers notifications/reminders for CO monitoring and can deliver monetary incentives (see below for screenshots). The UHC Accelerator program connected the VH business leads to the Quit For Life (QFL) smoking cessation program operated by Optum. Optum's QFL business has noted competitors who use CO monitoring as a cessation tool (e.g., Carrot, Inc.) and clients have asked why QFL does not offer CO monitoring as part of its program.

While there is preliminary research showing that smartphone-based CO monitoring is feasible, there is limited evidence that adding CO monitoring to a comprehensive cessation program increases cessation rates, engagement or satisfaction. The purpose of the present study is to conduct a pilot study examining the use of the VH monitoring device ("breath pen") and app as an adjunct to the evidence-based QFL program. Results from the pilot will be used to determine the need for further study of CO monitoring and may provide data for a grant application to conduct a larger RCT.

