Arm 1 receives CO monitoring device and instructions to download Vincere Health smartphone app. They will be asked to try out the Breath Monitor device to make sure they know how to use it and to call Vincere if they experience any issues. On day 60 they will be prompted to complete a CO breath test in the same way as Arms 2 and 3.

*Day 60*

**Follow-up Survey**: Participants will be sent information for completing the follow up survey via the Vincere app. \$20 will be added to the gift card total on the app after survey is completed.

**Biochemical Verification**: If participant self-reports being quit from tobacco at follow up, they will be asked to complete a final CO monitoring test (or tests) to verify quit status. Those who complete this final test will be given an additional \$20 via the app.

PROTOCOL

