#### 4.5. Data Sources and Variables

Research Question/Aim/Objective:	Data Variables:	Data Source

 
To determine eligibility
 
	
 
Enrollment screening
 
	
 
Service utilization (Apollo – Clinical Management System)
 

 
To determine tobacco quit outcomes
 
	
 
Baseline and follow-up survey
 
CO readings
 
	
 
Datstat (Survey software)
 
VH app & CO monitor
 

 
To determine satisfaction with the program
 
	
 
Follow up survey
 
Data from VH App
 
	
 
Service utilization (Apollo – Clinical Management System)
 
VH app & CO monitor
 

 
Treatment Engagement
 
	
 
Call completion
 
	
 
Service utilization (Apollo – Clinical Management System)
 

See screening and survey documents for full outline of data variables.

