#### 4.7. Statistical Methods

For the proposed pilot study we plan to use summary statistics with confidence intervals (CIs), means with standard errors (SE) and graphical displays (histograms, pie charts, Box plots, etc.) as appropriate to describe participant self-reported demographic characteristics, use of tobacco and other variables measured at baseline and at 2 months. We will use logistic or linear regression analyses to compare intervention and control groups on: mean number of calls completed; proportion completing at least two calls and, at 2 months, mean satisfaction ratings, mean change in cigarettes per day (cpd) and smoking cessation rates. We will conduct sensitivity analyses to determine the potential range of treatment effects on abstinence taking into account 1) different assumptions concerning the probability of relapse among survey non-responders, 2) substitution of biochemical results for those who claimed abstinence in the absence of agreement, and 3) the application of biochemical validation confirmation rate of abstinence to individuals who claimed abstinence but did not return their biochemical test results. Our analyses will include independent variables for state and gender to increase precision. We stratified randomization by state because of state variability and by gender because of the impact that gender has on treatment engagement and tobacco cessation. We will address missing values in three ways; 1) we will analyze responders only, 2) we will impute missing tobacco use as 'smoking' and 3) we will conduct sensitivity analyses (as discussed above) by modeling the proportion of smokers among non-respondents, and the applying of biochemical validation results to individuals who stated that they were abstinent.

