#### 4.9. Primary & Secondary Endpoints

Approximately 60 days after randomization, participants will complete an outcomes survey and a final CO test to determine smoking status. Participants will be sent information for completing the follow up survey via the Vincere app and email. Participants will be asked to complete a final CO monitoring test (or tests) to verify quit status.

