## 5.5. Participant Engagement, Results, & Withdrawal

All counseling calls will be attempted at least five times over different days. We will increase retention at the 2 month follow up survey by notifying participants via text message (on the app) that their survey is due. For those who do not complete the survey via the app, we will mail participants a print version of the survey along with a stamped return envelope. Print surveys will be mailed by the OCWR research team and returned to the Vincere Health office in Boston. Incentives will be given for survey completion. Strategies such as these have proven to be effective in our quitline research studies resulting in higher recruitment and retention rates.

Noted previously, participants are free to refuse to participate in any element of the study or treatment and to refuse to answer any question during the assessments with no repercussions. Study participants must request in writing to be withdrawn from the study and/or revoke their authorization to use their data. This information is outlined in the informed consent.

Participants will be restricted from re-enrolling into standard state quitline programs until their study activity is completed (whichever comes first of completion of final assessment and breath test, 90 days, or withdrawal from the study).

---

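### Do the unlisted app download and CO compliance rates of Aim 1 fall under a missing-value rule that would leave out non-users?

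*Combined protocol and SAP*

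**What the plan says.** Section 1, Aim 1, names the feasibility measures: "We hypothesize that the CO monitoring will be feasible and acceptable to deliver (measured by app download rates and CO compliance rates". It gives no denominator and no target.

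Section 4.7 says that regression will "compare intervention and control groups on: mean number of calls completed; proportion completing at least two calls and, at 2 months, mean satisfaction ratings", followed by change in cigarettes per day and cessation. Its descriptive summaries cover variables taken at baseline and at two months. Section 4.9 says only that "participants will complete an outcomes survey and a final CO test to determine smoking status". Download and daily testing appear in neither section.

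On missing data, 4.7 says: "We will address missing values in three ways; 1) we will analyze responders only, 2) we will impute missing tobacco use as" smoking. The third way is a set of sensitivity analyses on the proportion of smokers among those who did not respond and on biochemical confirmation of claimed abstinence.

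Section 2 says of the device: "It connects to smartphones via bluetooth and requires a dedicated app to compute and display CO levels". Section 4.2 (Day 60) says: "Participants will be sent information for completing the follow up survey via the Vincere app". Section 4.9 adds email as a second channel, and 5.4 makes an email address an entry requirement. Section 5.5 adds: "For those who do not complete the survey via the app, we will mail participants a print version of the survey".

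Section 4.5 lists CO readings as data, with the app and monitor as source, and says: "See screening and survey documents for full outline of data variables". Those documents were not available for this review.

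**The concern.** An aim whose two measures appear in neither the methods nor the endpoint section has no stated analysis. The open question is how to count participants who receive the device and never use it. They are the feasibility failures that Aim 1 should reveal.

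Of the three missing-value rules, only the first is worded without reference to tobacco. If it were taken to cover device use, non-users could drop out of the denominator. That might happen directly, because there is no CO level without the app. It might also happen indirectly, because the survey goes out first through the same app. A rate among users can never be lower than the rate among everyone offered monitoring, so such an error would favour a finding of feasibility. Section 4.13 makes product development depend partly on high compliance, and 4.6 says outcomes will guide the decision on further study.

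**Working it through.** **1. The schedule behind compliance.** Section 5.6 gives 2 tests a day, about 55 days and $1.50 a test. That is 55 × 2 = 110 tests, and 110 × 1.50 = $165, which reproduces the stated Arm 3 maximum. Section 4.1 sets a ceiling of 60 days, or 60 × 2 = 120 tests. Section 5.6 explains the difference by about five days of mailing. Someone who takes 110 tests is 100% compliant on the first count and 110/120 = 91.7% on the second. The choice rescales Arms 2 and 3 by the same factor and has no bearing on non-users.

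**2. Whom the first missing-value rule covers.** Earlier in 4.7, the sensitivity analyses refer to people who did not answer the survey. The rule stands beside two others that both deal with smoking status. Read together, a responder is someone who returned the two-month survey. Nothing in 4.7 connects the rule with download or daily testing.

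**3. Whether non-use is missing data.** Readings reach the study through the app and monitor (4.5), and Arm 3 is paid per test (4.1, 5.6), so tests must be counted. A participant with no reading has a count of zero. A missing-value rule has nothing to act on.

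**4. The users-only reading.** Let a be the share who ever use the device. Users-only compliance divided by all-randomised compliance is 1/a: 1.11 at 90%, 1.43 at 70% and 2.00 at 50% (range assumed). These factors are correct arithmetic, but they describe an analysis that no section proposes. On this reading the download rate would be a/a = 100% whatever happened, so the rule cannot sensibly be meant that way.

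**5. The survey-responder reading, if someone did apply it.** Let d be the share who download, c the mean compliance among users, and r_u and r_n the survey response of users and non-users. Then

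- download among responders = d·r_u / (d·r_u + (1 − d)·r_n)
- compliance among responders = c × that share

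Assume d = 0.70, c = 0.60 and r_u = 0.80. The all-randomised values are 70% and 0.70 × 0.60 = 42%.

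| r_n | download among responders | compliance among responders |
|---|---|---|
| 0.80 | 0.56/0.80 = 70% | 42% |
| 0.60 | 0.56/0.74 = 75.7% | 45.4% |
| 0.40 | 0.56/0.68 = 82.4% | 49.4% |
| 0.20 | 0.56/0.62 = 90.3% | 54.2% |
| 0 | 0.56/0.56 = 100% | 60% |

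All non-users drop out only in the last row, where none of them answers. The email notice and the mailed print survey exist to prevent that.

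**6. Scale.** With 350 participants split equally (ratio not stated, so assumed), an arm has about 116.7. The largest possible 95% half-width for a mean of values between 0 and 100% is 1.96 × √(0.25/116.7) = 9.1 points. In the rows with r_n of 0.60, 0.40 and 0.20 the compliance error is 3.4, 7.4 and 12.2 points. A misapplied rule would therefore not be trivial, and the case turns on whether the plan applies it.

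**The case for a change.** The strongest case for a change is that both rates are missing from the two sections where an analyst would look, and that 4.5 has no row for Aim 1. Section 4.13 acts on high compliance without saying what counts as high, so leaving the denominator open until data are in hand allows a favourable choice. Sections 4.3 and 4.8 describe the follow-up survey as delivered through the app, so lower response among non-users is plausible. A definition would cost a few lines of text.

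The omission stands, and so does the direction of the hypothetical error. The rest is weaker. Section 4.13 also requires signs of better quit rates, engagement or satisfaction, so inflated compliance alone would not meet it. Aim 1 asks whether monitoring can be delivered, which already points to everyone assigned to it as the denominator. A definition fixed in advance would not be neutral either. With 110 tests as denominator, a device that arrives on day 10 caps a perfect complier at (60 − 10) × 2 = 100 tests, or 100/110 = 90.9%, so slow mailing would count as non-compliance. Using a first CO reading in place of download would merge two things that Aim 1 lists separately.

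**Conclusion.** The gap is real but it is missing detail, and no stated rule has been shown to give a wrong result. The responders-only rule concerns the survey, non-users have routes other than the app by which to answer it, and absence of readings is an observed zero. The factors of 1.11 to 2.00 belong to an analysis that the plan does not contain. The upward shift on the survey reading (42% to between 45% and 54% in the example) needs two things together: a use of the rule that 4.7 does not state, and lower survey response among non-users. With equal response the shift is zero.

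This rests on reading 4.7 as a whole and on the app and monitor yielding a test count for each participant. Every uptake, compliance and response figure above is assumed. No section says that download itself is logged, and the screening and survey documents may say more. In an unpowered pilot, analysts would probably report both rates by arm among all randomised to Arms 2 and 3 and state the denominator. No change to the plan follows.

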### Aim 2 + Hypothesis 2:

Conduct a 3-arm randomized pilot study to determine the value of adding CO monitoring (with and without financial incentives) to standard Quit For Life tobacco cessation service offerings. We hypothesize that the CO monitoring will increase engagement in quitline treatment (measured by calls completed).

### Aim 3 + Hypothesis 3:

Conduct a 3-arm randomized pilot study to determine the value of adding CO monitoring (with and without financial incentives) to standard Quit For Life tobacco cessation service offerings. We hypothesize that the CO monitoring will increase tobacco cessation and satisfaction rates compared with treatment as usual (TAU). We will also examine cost effectiveness of the intervention as compared to TAU.

## 2. BACKGROUND & SIGNIFICANCE

Carbon Monoxide (CO) is an invisible, odorless, but toxic gas that is formed during tobacco smoking and can be measured in the exhaled air of smokers using CO monitors. CO levels, measured as particles per million (ppm), can help distinguish between different levels of smoking, with levels below 10 ppm commonly used as indicators of abstinence. CO testing acts as an objective non-invasive measure of harm from exposure to smoking and conveys more information than that provided by the number of cigarettes smoked alone (e.g., CO levels can be affected by the intensity with which cigarettes are smoked). Exposure to CO via smoking is associated with incidents of stroke and other cardiovascular diseases. CO levels are not affected by concurrent use of nicotine-containing products such as e-cigarettes or nicotine replacement which increases its value as a testing tool for smoking cessation studies and, thus, CO testing is widely used in research as an outcome measurement.

## PROTOCOL

CO testing has also been identified as a valuable monitoring and feedback component of effective stop smoking programs and benefits cessation through making the health impact of smoking more salient. Smaller and more affordable CO monitors have made CO monitoring feasible for home use. The iCOTM Smokerlyzer® manufactured by Bedfont® Scientific Ltd. (Harrietsham, UK) is currently the only such device available for purchase. It connects to smartphones via bluetooth and requires a dedicated app to compute and display CO levels. This provides momentary feedback on behavioral outcomes, which are important self-regulatory and behavior change techniques in smoking cessation. Preliminary research suggests that personal use of CO monitors is acceptable, valued and potentially highly motivating for smokers. No large scale studies of CO monitoring as a component of a comprehensive tobacco cessation program have been published.

**Vincere Health (VH; [www.vincere.health](http://www.vincere.health))** is a small business who joined United Healthcare's (UHC) Accelerator program in 2020. VH has developed a proprietary smartphone app that transforms data from the Bedfont CO monitor (cited above) into user-friendly pictorial displays and graphs. The app also connects to coaches, offers notifications/reminders for CO monitoring and can deliver monetary incentives (see below for screenshots). The UHC Accelerator program connected the VH business leads to the Quit For Life (QFL) smoking cessation program operated by Optum. Optum's QFL business has noted competitors who use CO monitoring as a cessation tool (e.g., Carrot, Inc.) and clients have asked why QFL does not offer CO monitoring as part of its program.

While there is preliminary research showing that smartphone-based CO monitoring is feasible, there is limited evidence that adding CO monitoring to a comprehensive cessation program increases cessation rates, engagement or satisfaction. The purpose of the present study is to conduct a pilot study examining the use of the VH monitoring device ("breath pen") and app as an adjunct to the evidence-based QFL program. Results from the pilot will be used to determine the need for further study of CO monitoring and may provide data for a grant application to conduct a larger RCT.

The state of Maryland's tobacco cessation quitline is operated by Optum and the Maryland Department of Health has partnered with Optum to conduct this study with its quitline's participants. They have signed an agreement to that effect. The participant pool for this pilot is Maryland residents who call the tobacco quitline wanting to enroll in a quit smoking program.

This study is funded by Optum's QFL program and participating states (currently Maryland). Scientific oversight is provided by [name], Principal scientist at the Optum Center for Wellbeing Research.

## 4. RESEARCH DESIGN & METHODS

### 4.1. General Design

Quitline registration agents will screen callers for study eligibility criteria during the state quitline enrollment process. Interested and eligible participants will be transferred to a research trained quitline coach who will conduct the informed consent discussion. After giving verbal consent, participants will complete the baseline assessment and be randomized to one of 3 arms: quitline treatment as usual, quitline plus CO monitoring or quitline plus CO monitoring and financial incentives. Participants will complete coaching calls. Approximately 60 days after randomization, participants will complete an outcomes survey and all participants will complete a final CO test to determine smoking status.

**Interventions**-There will be three treatment arms in this trial:

**Arm 1:** Standard quitline (treatment as usual: TAU). This arm consists of the state quitline services as offered by participating states (currently MD). These state quitlines offer five proactive coaching calls, mailed support materials, access to text messaging and web-based supplemental programs, plus at least two weeks of free nicotine replacement (NRT). This arm will be mailed a personal CO monitor device and be instructed to download the Vincere Health smartphone app 60 days after randomization in order to complete the final outcome assessment.

**Arm 2:** TAU plus CO monitoring. Participants in this arm will receive all treatment component of TAU. They will also receive a personal CO monitor by mail immediately after study enrollment and they will be instructed to download the Vincere Health CO Monitoring App. The app will lead participants through a 2x/day CO monitoring program via the Vincere Health Breath Monitor - CO Monitoring device used in conjunction with the smartphone app. The app includes providing CO monitoring results and visualizations of CO results over time as well as reminders and reinforcement for compliance with the CO monitoring program.

**Arm 3:** TAU plus CO monitoring plus financial incentives. Participants in this arm will received all intervention components described above for Arms 1 & 2. In addition, they will receive financial incentives for engagement with the CO monitoring program. They will receive up to \$1.50 for each use of the CO monitor (up to 2x per day for up to 60 days). Incentives will accrue and be visible on the app. Incentives will be delivered by gift card of the participant's choice.

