## 5.6. Compensation / Remuneration / Reimbursement

**Research Incentives:** Participants will receive \$15 for completing the baseline survey, \$20 for completing the outcome survey and \$20 for completing the final CO test (biochemical verification of smoking status). These incentives will be provided to all participants.

**Intervention incentives:** Participants in Arm 3 will also be able to earn incentives for CO monitoring compliance. They will earn \$1.50 for each test and asked to complete 2 tests per day (\$3 per day). During the 60 day study period, participants will have about 55 days of CO monitoring in which to earn incentives (we anticipate approximately 5 days for mailing the device). 55 days with \$3 per day incentives means Arm 3 participants could earn up to \$165 for CO monitoring compliance. This amount is in line with previous financial incentive for tobacco cessation research.

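### Sections 4.1 and 4.2 give different days for the control arm's CO monitor and app; as worded, section 4.1 leaves Arm 1 no set-up time before the day 60 breath test

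*Combined protocol and SAP*

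**What the plan says.** Section 4.1 (General Design), describing Arm 1: "This arm will be mailed a personal CO monitor device and be instructed to download the Vincere Health smartphone app 60 days after randomization". The stated purpose is the final outcome assessment.

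Section 4.2 (Study Measures & Methods), under Day 55: "Arm 1 receives CO monitoring device and instructions to download Vincere Health smartphone app". It continues: "They will be asked to try out the Breath Monitor device to make sure they know how to use it", with a referral to the app company for any problems, and then: "On day 60 they will be prompted to complete a CO breath test in the same way as Arms 2 and 3".

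Five other places bear on the timing:

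- Section 4.1 sets the assessment only loosely: "Approximately 60 days after randomization, participants will complete an outcomes survey and all participants will complete a final CO test".
- Section 4.2, under Day 60, ties the test to a self-report of having quit. For those participants, "they will be asked to complete a final CO monitoring test (or tests) to verify quit status".
- Section 5.6, in the Arm 3 incentive calculation: "we anticipate approximately 5 days for mailing the device".
- Section 2 states that the monitor cannot compute or display a CO level without its app.
- Section 5.5 bars re-enrollment in the standard quitline until the final assessment and breath test are done, 90 days have passed, or the participant withdraws, whichever is first.

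**The concern.** Arm 1 does not use the monitor as treatment. It gets the device and app only so that its outcome can be measured. Arms 2 and 3 have had theirs for weeks by then. Most of that difference in familiarity is inherent in the design, and the Day 55 try-out is the step section 4.2 provides to offset it.

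If staff follow section 4.1 instead, the outcome device or its app reaches controls on or after the nominal test day, in that arm alone. CO-verified abstinence is a listed outcome in the measures table, and section 4.7 compares cessation rates between arms. Verification that is later or less complete only in controls would weaken the comparison. If claimants without a test were counted as unverified, it would tilt the comparison toward the CO arms.

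The pilot is not powered for a difference, but section 4.6 says its outcomes will be used to decide on further study.

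**Working it through.** This is calendar arithmetic.

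**Inputs**
- Arm 1 device and app: 60 days after randomization (section 4.1) or Day 55 (section 4.2).
- Test prompt: day 60 (section 4.2).
- Mailing time: about 5 days (section 5.6). It is stated for Arm 3, and applying it to Arm 1 is an assumption. A range of 3 to 7 days is also assumed, to show sensitivity.

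**The plan's own figure.** Section 5.6 allows 60 - 5 = 55 monitoring days, and 55 × 2 × $1.50 = $165. Both figures reproduce.

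**Set-up days = 60 - day on which both device and app are available**

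| Text followed | Device and app available | Set-up days before day 60 |
|---|---|---|
| 4.2, arrival on Day 55 | day 55 | 60 - 55 = 5 |
| 4.1, mailed at day 60 | 60 + 5 = day 65 (63 to 67) | 60 - 65 = -5 (-3 to -7) |
| 4.1, only the app instruction at day 60 | day 60 | 60 - 60 = 0 |

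The third row is zero however early the device is mailed, because the device gives no reading without the app. The app date also still conflicts with Day 55.

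**If Day 55 in section 4.2 were the mail-out day,** arrival would be 55 + 5 = day 60, leaving no set-up days. With mailing of 4 days or less it would leave 1 to 4 days.

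**Day-numbering check.** If randomization is counted as Day 1, the three rows become 5, -6 and -1. The conclusion is unchanged.

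**Comparison with the other arms.** Arms 2 and 3 have the device from about day 5, so 60 - 5 = 55 days of use by day 60. Arm 1 has about 5 under the Day 55 schedule.

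**Mail-out needed for receipt by Day 55:** 55 - 5 = day 50.

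**The case against.** The best defence is that section 4.2 is the detailed schedule and is coherent. It says Arms 2 and 3 are *sent* the device but that Arm 1 *receives* it, which favours arrival at Day 55. On that view section 4.1 is a loose summary needing a one-line correction. The point about section 4.2 stands. It does not remove the conflict, because section 4.1 is current text that staff could follow.

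The consequence is also limited:

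- Nothing makes day 60 a cut-off. The 90-day limit in section 5.5 governs re-enrollment and is not a test window, but it shows that breath tests were expected to run past day 60. A device arriving at day 65 leaves about 90 - 65 = 25 days.
- Section 4.7 names biochemical results only in sensitivity analyses, one of which covers claimants without a test. That addresses missing tests, but not tests taken later in one arm.
- The print survey in section 5.5 protects self-report, though it cannot replace a breath test.
- Test days can vary in every arm, because section 4.2 requests the test after a self-report of quitting.

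A reader might infer that most interpretations of the two sections leave controls no set-up time, and count them to say so. The count is not sound. The interpretations are not equally plausible, Day 55 as mail-out being the weaker reading of section 4.2, and the tally changes if mailing takes 4 days or less. A reader might also infer that following section 4.1 does away with the try-out or makes testing impossible. The documents do not support that, since a late device delays the try-out and a participant could still try it before a later test.

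**Conclusion.** The conflict between sections 4.1 and 4.2 is real and rests on no assumption. Section 4.1 is the text that does not fit. As worded it puts the device with controls near day 65, about 10 days later than section 4.2 (65 - 55), or leaves zero set-up days if only the app instruction falls at day 60. The day 65 figure assumes that the approximate 5-day mailing time for Arm 3 also applies to Arm 1.

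The likely result of following section 4.1 is that some verification tests come later, or are missing, in the control arm only. The documents give no basis for sizing an effect on test completion or abstinence, and none is claimed. Aims 1 and 2 (feasibility and call engagement) do not depend on the Arm 1 shipping day. The change should be made because it is cheap and the exposure falls on one arm.

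**What to change.** 1. Reconcile section 4.1 with the Day 55 schedule in section 4.2. State the Arm 1 mail-out day separately from the receipt and app-instruction day, so that device and app are in hand by Day 55. With 5-day mailing, mail-out is at about day 50.
2. Define one window for the verification CO test, in days from randomization, common to all three arms.
3. Report test completion and day of test by arm.

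The cost is one protocol clarification and a little extra reporting. No more devices and no new participant procedures are needed. If shipments already arrive by Day 55, the shipping trigger does not change. If follow-up is already complete, recording the actual shipping dates and reporting test day by arm would still let readers judge whether the arms were comparable.
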